
Appendix B: Imputation Rules for Missing Prior/Concomitant Medication Dates

Imputation rules for missing or partial medication start/stop dates are defined below:

1. Missing or partial medication start date:
 - a. If only DAY is missing, use the first day of the month.
 - b. If DAY and Month are both missing, use the first day of the year.
 - c. If DAY, Month and Year are all missing, use a date before the first dose date (in practical, use Jan. 01, 2000 to impute).
2. Missing or partial medication stop date:
 - a. If only DAY is missing, use the last day of the month.
 - b. If DAY and Month are both missing, use the last day of the year.
 - c. If DAY, Month and year are all missing, assign ‘continuing’ status to stop date (in practical, use Dec. 31, 2050 to impute).

In summary, the prior, concomitant, or post categorization of a medication is described below.

Medication Stop Date		
Medication Start Date	< First Dose Date of Study Drug	≥ First Dose Date and ≤ End Date of Part 1 TE Period
< First dose date of study drug	P	PC
≥ First dose date and ≤ End date of Part 1 TE period	-	C

P: Prior; C: Concomitant during the Part 1 TE period

Imputation rules for missing and/or partial dates of non-pharmacological treatment/procedure will follow the same imputation rule.

Appendix C: Imputation Rules for Missing AE dates

Imputation rules for missing or partial AE start date are defined below. If the imputed AE start date is before the informed consent date, the AE start date will be imputed using the study informed consent date.

- **If only Day of AE start date is missing:**

- If the full (or partial) AE end date is NOT before the first dose date of the Treatment Period or AE end date is missing, then
 - if AE start year and month are equal to the month and year of first dose date of the Treatment Period, then impute the AE start day as the day of first dose date of the Treatment Period;
 - else impute the AE start day as 1.
- else impute the AE start day as 1.

Compare the imputed AE start date with Part 1 TE period or cumulative safety period to determine whether the AE is pretreatment AE, TEAE during the Part 1 TE Period, TEAE during the Cumulative Safety Period, or post-treatment AE.

- **If Day and Month of AE start date are missing:**

- If the full (or partial) AE end date is NOT before the first dose date of the Treatment Period or AE end date is missing, then
 - if AE start year is equal to the year of first dose date of the Treatment Period, then impute the AE start month and day as the month and day of first dose date of the Treatment Period;
 - else impute the AE start month as January and day as 1.
- else impute the AE start month as January and day as 1.

Compare the imputed AE start date with Part 1 TE period or cumulative safety period to determine whether the AE is pretreatment AE, TEAE during the Part 1 TE Period, TEAE during the Cumulative Safety Period, or post-treatment AE.

- **If Year of AE start date is missing:**

If the year of AE start is missing or AE start date is completely missing then query site and

- If the full (or partial) AE end date is NOT before the first dose date of the Treatment Period or AE end date is missing, then impute the AE start date as the date of first dose date of the Treatment Period.
- else impute AE date as the informed consent date.

The imputation should ensure the imputed AE start date is not before the informed consent date.

- Imputation rules for partial AE end date are defined below:

If partial end date, then impute as min (the last day of the month, end of study participation (of Part 1)) if day is missing, or min (Dec, end of study participation (of Part 1)) if month is missing.

Appendix D: Criteria for Threshold Analysis

Table 12-3 Threshold Analysis Criteria for Laboratory Tests (as applicable)

Parameter	Categorical change	Comments
Clinical Chemistry (LFT)		
ALT	≤3xULN >3x - ≤ 5xULN >5x - ≤ 8xULN >3xULN >5xULN >8xULN	FDA DILI Guidance Jul 2009.
AST	≤3xULN >3x - ≤ 5xULN >5x - ≤ 8xULN >3xULN >5xULN >8xULN	FDA DILI Guidance Jul 2009.
ALT or AST	ALT>3xULN or AST>3xULN ALT>5xULN or AST>5xULN ALT>8xULN or AST>8xULN	Vertex LFT working group 2014
Alkaline Phosphatase	>1.5xULN	FDA DILI Guidance Jul 2009.
Total Bilirubin	>1.5x - ≤2xULN >2xULN	FDA DILI Guidance Jul 2009.
Direct Bilirubin	>ULN - ≤ 1.5xULN >1.5 - ≤ 2xULN >2 - ≤ 3xULN >3 - ≤ 10xULN >10xULN	FDA DILI Guidance Jul 2009.
ALT and Total Bilirubin	ALT>3xULN and TBILI>2xULN	FDA DILI Guidance Jul 2009. To be counted within a same treatment phase, whatever the interval between measurements.
AST and Total Bilirubin	AST>3xULN and TBILI>2xULN	FDA DILI Guidance Jul 2009. To be counted within a same treatment phase, whatever the interval between measurements.
(ALT or AST) and Total Bilirubin	(ALT>3xULN or AST>3xULN) and TBILI>2xULN	Vertex LFT working group 2014
GGT	>ULN - ≤ 2.5xULN >2.5 - ≤ 5.0xULN >5.0 - ≤ 20.0xULN >20.0xULN	CTCAE grade 1-4
Clinical Chemistry (Non-LFT)		
CPK (Creatine kinase)	>3x - ≤ 10xULN >10xULN	FDA criteria Feb 2005. Am J Cardiol April 2006.
Albumin	≤25 g/L	

Table 12-3 Threshold Analysis Criteria for Laboratory Tests (as applicable)

Parameter	Categorical change	Comments
Creatinine	≥150 µmol/L (Adults) ≥30% change from baseline ≥100% change from baseline	Benichou C., 1994.
Blood Urea Nitrogen	≥17 mmol/L	
Chloride	<85 mmol/L >115 mmol/L	
Sodium	≤129 mmol/L ≥150 mmol/L	
Potassium	<3 mmol/L ≥5.5 mmol/L	FDA Feb 2005.
Amylase	>1x - ≤ 1.5xULN >1.5x - ≤ 2xULN >2x - ≤ 5xULN >5xULN	Criteria based upon CTCAE
Lipase	>ULN - ≤ 1.5xULN >1.5x - ≤ 2xULN >2x - ≤ 5xULN >5xULN	Criteria based upon CTCAE
Total protein	<LLN >ULN	No CTCAE
Glucose		
Hypoglycaemia	≤3.9 mmol/L and <LLN	ADA May 2005.
Hyperglycaemia	≥11.1 mmol/L (unfasted); ≥7 mmol/L (fasted)	ADA Jan 2008.
Hematology		
WBC (Leukocytes)	<3.0 Giga/L (Non-Black); <2.0 Giga/L (Black) ≥16.0 Giga/L	Increase in WBC: not relevant. To be interpreted only if no differential count available.
Lymphocytes	>4.0 Giga/L	
Neutrophils	<1.5 Giga/L (Non-Black); <1.0 Giga/L (Black)	International Consensus meeting on drug-induced blood cytopenias, 1991. FDA criteria.
Monocytes	>0.7 Giga/L	
Basophils	>0.1 Giga/L	
Eosinophils	>0.5 Giga/L or >ULN (if ULN ≥ 0.5 Giga/L)	Harrison- Principles of internal Medicine 17th Ed., 2008.
Hemoglobin	≤115 g/L (Male); ≤95 g/L (Female) ≥185 g/L (Male); ≥165 g/L (Female) Decrease from Baseline ≥20 g/L	Criteria based upon decrease from baseline are more relevant than based on absolute value. Other categories for decrease from baseline can be used (≥30 g/L, ≥40 g/L, ≥50 g/L).
Platelets	<100 Giga/L ≥700 Giga/L	International Consensus meeting on drug-induced blood cytopenias, 1991.

Table 12-3 Threshold Analysis Criteria for Laboratory Tests (as applicable)

Parameter	Categorical change	Comments
Reticulocytes/Erythrocytes (%)	<LLN >ULN	No CTCAE

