## 8.2 Exclusion Criteria

1. History of any illness or comorbidity reviewed at the Screening Visit that, in the opinion of the investigator, might confound the results of the study, interfere with or pose an additional risk in conducting the study assessments, or pose an additional risk in administering study drug to the subject. For example, a history of cirrhosis with portal hypertension, or prior allergic reaction to gadolinium (Gd)-based contrast material, or metallic implants incompatible with MRI.
2. Any clinically significant laboratory abnormalities at the Screening Visit that would interfere with the study assessments or pose an undue risk for the subject (as deemed by the investigator).
3. Any of the following abnormal laboratory values at the Screening Visit:
  - Hemoglobin <10 g/dL
  - Alanine transaminase (ALT), aspartate transaminase (AST), or total bilirubin >2 × upper limit of normal (ULN)
  - Abnormal renal function defined as glomerular filtration rate  $\leq 45$  mL/min/1.73 m^2 (calculated by the Bedside Schwartz equation)
4. An acute upper or lower respiratory infection, PEx as defined by the investigator, or changes in therapy (including antibiotics) for pulmonary disease within 28 days before Day 1 (first dose of study drug).
5. Any clinically significant "non-CF-related" illness within 2 weeks before Day 1. "Illness" is defined as an acute (serious or nonserious) condition (e.g., gastroenteritis).
6. History of solid organ or hematological transplantation.
7. Ongoing or prior participation in an investigational drug study (including studies investigating LUM and/or IVA) within 30 days of the Screening Visit.
  - A washout period of 5 terminal half-lives of the previous investigational study drug, or 30 days, whichever is longer, must elapse before the Screening Visit.
  - The duration of the elapsed time may be longer if required by local regulations.

Note: Ongoing participation in a noninterventional study (including observational studies) is permitted.
8. Use of restricted medication or food within specified duration before the first dose of study drug as defined in Section 9.4.
9. Inability of the subject to perform the multiple-breath washout (MBW) assessment during the Screening Period (Section 11.4.2).

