#### **12.3.4.2 Clinical Laboratory Assessments**

For the treatment-emergent laboratory measurements, the raw values and change from baseline values of the continuous laboratory parameters will be summarized in SI units by treatment group at each scheduled time point. In addition, mean value at each visit will be plotted by treatment groups for each of the liver function parameters.

The number and percentage of subjects with at least 1 categorical change during the TE Period will be summarized by treatment group. The categorical (post-baseline) shift from baseline will also be summarized for selected laboratory parameters. The categorical criteria and the parameter selection criteria will be provided in the SAP. In addition, a listing containing individual subject laboratory assessment values outside the reference ranges will be provided. This listing will include data from scheduled and unscheduled time points.

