9.2.3.2 Clinical Laboratory

For the treatment-emergent laboratory assessments during the Part 1 TE period, the observed values and change from study baseline of the continuous hematology and chemistry results will be summarized in SI units at each visit by treatment group.

The number and percentage of subjects meeting at least 1 threshold analysis criterion during the Part 1 TE period will be summarized by treatment group. The threshold analysis criteria are provided in [Appendix D](#).

In addition, a listing containing individual subject hematology and chemistry values during the Part 1 TE period will be provided with a column indicating outside reference range or not. This listing will include data from both scheduled and unscheduled visits.

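### The absolute low-hemoglobin criterion takes no account of baseline, and its male limit (115 g/L) lies above the entry floor (100 g/L), so some boys are counted with no change while girls with the same values are not

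*SAP*

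**What the plan says.** - **Limits.** The hemoglobin row of SAP Table 12-3 (Appendix D) gives low limits of "≤115 g/L (Male); ≤95 g/L (Female". It is the only row split by sex. The same row adds "Decrease from Baseline ≥20 g/L", with the comment "Criteria based upon decrease from baseline are more relevant than based on absolute value".
- **Counting rule, Part 1.** SAP 9.2.3.2: "The number and percentage of subjects meeting at least 1 threshold analysis criterion during the Part 1 TE period will be summarized by treatment group". Nothing requires that the criterion was not met at baseline. Under SAP 8.2 the period starts at first dose.
- **Counting rule, Part 2.** SAP 9.3.3.2 uses the same count for the Part 2 Safety Period. SAP 9.3.3 presents it for the overall LUM/IVA group.
- **Entry criterion.** Protocol 8.2, exclusion 3, excludes "Hemoglobin <10 g/dL", with no distinction by sex.
- **Shift summary.** Protocol 12.3.4.2: "The categorical (post-baseline) shift from baseline will also be summarized for selected laboratory parameters". It leaves the choice of parameters to the SAP. Neither SAP 9.2.3.2 nor 9.3.3.2 describes a shift summary.
- **Creatinine.** One limit in Table 12-3 is labelled for adults, "≥150 µmol/L (Adults"). The row also has two percent-change criteria, and the table is headed as applying where applicable.

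**The concern.** A threshold count in a safety table is normally read as the number of children who became abnormal on treatment. An absolute limit that takes no account of baseline measures status, not change. That does little harm when the limit lies below the lowest value allowed at entry, because a child must then fall to reach it. It matters when the limit lies above the entry floor, because a child can meet the criterion at the first post-dose test without having changed.

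For hemoglobin, the male limit is above the floor and the female limit is below it. The row therefore partly reports which boys came in with lower values, and it treats boys and girls with identical results differently. In Part 1 a reader can at least compare arms. In Part 2 all children receive LUM/IVA, and a count that includes unchanged boys has nothing beside it to show what would be expected without drug.

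**Working it through.** The plan derives no figure from these limits, so there is none to reproduce. The check is a unit conversion, a comparison of rules, and an illustration under stated assumptions.

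**1. Limits against the floor.** 10 g/dL × 10 = 100 g/L. Male limit: 115 − 100 = 15 g/L above the floor. Female limit: 95 − 100 = 5 g/L below it. A girl at the floor must fall by at least 5 g/L to be counted; a boy anywhere from 100 to 115 g/L need not fall at all.

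**2. The rules applied to single children (g/L).**

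| Baseline → on treatment | Boy, absolute limit | Girl, absolute limit | Fall ≥20 |
|---|---|---|---|
| 110 → 110 (no change) | counted | not counted | no |
| 115 → 96 (fall 19) | counted | not counted | no |
| 116 → 96 (fall 20) | counted | not counted | yes |
| 110 → 92 (fall 18) | counted | counted | no |

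The first row is the defect. The fall criterion is a separate entry and does not take that boy out of the absolute count. The second row is chosen to sit just inside both limits and shows only where the edges lie.

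**3. Expected number counted with no change.** Assumptions: half the children are boys, and a fraction f of them enter at 100 to 115 g/L, with f from 0.10 to 0.30.

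- All 50 children: 50 × 0.5 × f = 2.5 to 7.5.
- LUM/IVA in Part 1: 33 × 0.5 × f = 1.65 to 4.95.
- Placebo in Part 1: 17 × 0.5 × f = 0.85 to 2.55.

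The expected percentage, 5% to 15%, is the same in both arms.

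**4. Repeated testing.** Step 3 holds each child's value fixed. With four scheduled post-baseline hematology visits in Part 1 (Weeks 12, 24, 36 and 48), ordinary variation adds to the count. A normal simulation with no drug effect used one screening value of at least 100 g/L, the same distribution for both sexes, an assumed mean of 115 to 130 g/L, an SD of 8 to 10, and a within-child correlation of 0.5 to 0.8. Ranges over the scenarios:

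| Quantity, share of eligible children of that sex | Range |
|---|---|
| Boys at or below 115 g/L at baseline | 3.1% to 48.5% |
| Boys with at least one of four values at or below 115 g/L | 6.9% to 79.5% |
| Boys above 115 g/L at baseline with at least one such value later | 4.5% to 35.6% |
| Girls with at least one value at or below 95 g/L | 0.0% to 5.3% |
| Any fall of at least 20 g/L | 0.0% to 7.6% |

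In one middle scenario (mean 120, SD 10, correlation 0.8), 47.0% of boys and 0.7% of girls are counted, although both sexes have the same hemoglobin. The ranges are wide because the inputs are unknown. The direction does not depend on them.

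**5. What a baseline condition alone would do.** It removes the unchanged boys. It would also hide the boy who goes from 110 to 92 g/L: he already met the limit, and a fall of 18 g/L is below 20. In step 4 it still leaves 4.5% to 35.6% of boys counted with no drug effect. So a baseline condition needs a shift table beside it, and the limit itself needs attention.

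**The case against.** The case for leaving the table alone has substance.

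- **Baseline is not ignored throughout.** A reader might infer that the threshold analysis disregards baseline altogether. It does not: the hemoglobin row has a fall criterion, which the SAP prefers, and creatinine has two percent-change criteria. Only the absolute limits lack a baseline condition.
- **The table is not shown to be an adult table.** Only the creatinine limit carries that label, and by that label it miscounts no child. The documents do not say that 115 and 95 g/L are adult values. Many other rows are multiples of the laboratory's own limits.
- **Not all eligible boys are affected, and none is counted before dosing.** Only boys at 100 to 115 g/L can be counted while unchanged, and counting starts at first dose.
- **An entry floor is a safety exclusion, not a limit of normal.** An analysis limit above it does not contradict the protocol. A hemoglobin shift table was not specifically promised either, since the selection was left to the SAP.
- **Arm imbalance is not bias.** With 33 against 17 children and the assumptions of step 3, chance gives a difference of at least 10 percentage points with probability 0.105, 0.238 or 0.326 for f = 0.1, 0.2 or 0.3. That is sampling noise that any binary row would show at this size.
- **Other outputs help.** SAP 9.2.3.2 also gives observed values and change from baseline by visit, and a listing that marks values outside the reference range. Safety is descriptive, without confidence intervals.

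These points narrow the concern and lower its priority. They do not remove the unchanged boys from the absolute count, make the sex split consistent with a common entry floor, or supply a shift summary where the SAP laboratory sections have none.

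**Conclusion.** The concern holds for the absolute low-hemoglobin criterion. The limits, the floor and the counting rule are all in the documents, and together they count a stable boy at 100 to 115 g/L but not a girl with the same values.

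The size is unknown. The figure of 2.5 to 7.5 of 50 children rests on the assumed share of boys and the assumed 10% to 30% in the band, and the simulation rests on assumed means, SDs and correlations. In Part 1 the inflation is expected equally in both arms, so it blurs the comparison but does not favour an arm. It matters more in Part 2, where the count stands alone.

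The documents do not support the wider reading that the whole table is adult-based or blind to baseline. The primary analysis is untouched. Priority is minor to moderate.

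**What to change.** 1. **SAP 9.2.3.2 and 9.3.3.2:** report absolute criteria as newly met, that is, met on treatment and not met at the applicable baseline (study baseline in Part 1, LUM/IVA baseline in the final analysis).
2. **Same sections:** add the categorical shift-from-baseline table foreseen in Protocol 12.3.4.2 and name hemoglobin among its parameters. Give hemoglobin at least two bands on the low side, since with a single low band a worsening from an already low baseline would appear as no shift.
3. **Table 12-3:** replace the sex-split low-hemoglobin limits with one analysis limit for both sexes suited to ages 2 to 5, for example the central laboratory's age-specific reference limit, and state its source. That limit is not in the documents and may itself lie above 100 g/L, so items 1 and 2 are still needed. Keep the fall-from-baseline criterion.
4. **Tidy-up only:** remove the creatinine limit labelled for adults and keep the percent-change criteria.

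The cost is an edit to two SAP sections and one appendix row, one derived baseline flag and one extra table. If Table 12-3 is a standard table of the sponsor, the change departs from it and makes comparison with other studies slightly less direct. No new data are needed, and the entry criterion is not in question.
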